### Strata

Strata A = Low CAR, Low Kellgren- Lawrence

Strata B =High CAR, Low Kellgren- Lawrence

Strata C= Low CAR, High Kellgren- Lawrence

Strata D= High CAR, High Kellgren- Lawrence

The unblinded investigator, [name], will pull the next envelope from the appropriate strata after the patient visit is confirmed and as close to the visit as possible to allow for adequate setup time. Before randomizing a participant the investigator will confirm that a cancelation email or message has been received. Again the goal is to avoid randomizing a participant that eventually drops out of the study to a treatment group. Following randomization the envelop will be shredded by the unblinded investigator.

### 3.h Blinding and Unblinding

The current study is a double-blinded randomized controlled trial, where the investigators evaluating study outcomes as well as patients in the TENS+TE and Sham TENS + TE groups will be blinded. There will be no effort to blind patients in the control or TE only group.

The unblinded personnel in the study will be [name] (in charge of back-up randomizations lists), [name] (in charge of screening, randomization and scheduling), [name] (in charge of screening, randomization and scheduling), and [name] (in charge of initial randomization and study analysis). All efforts will be made to maintain the blinding of all other study personnel collecting data as well as the patients in the study. We will assess blinding of patients and study personnel at the end of the study to determine efficacy of the blinding procedures. We will not unblind any of the blinded personnel until after the study has been completed and all outcome measures for all patients have been analyzed and imputed into databases.

We will unblind the patients if: 1) they sustain a medical condition that requires that they know their group assignment or 2) they request the information in writing following the completion of the project in that all outcome measures for all patients have been analyzed and imputed into databases.

### **3.i Participant Evaluations and Follow-up**

#### **3.i.1 Timeline and Visit Schedule**

Once the Patient is enrolled in the study there are three testing sessions that will be conducted in the Sports Medicine Research Laboratory (Baseline, Follow-up 1 [4-weeks] and Follow-up 2 [8-weeks]). In addition there are data that will be collected in the physical therapy clinic before the therapeutic exercise session begins on the last session of each week. The schedule of when evaluations take place must be specified in the second row of the Timeline (Appendix A).

#### **3.i.2 Scope**

Outcome Measures are sectioned into Consent and Demographics, Self-reported outcomes, strength, function & gait and intervention outcomes. On baseline and follow-up testing performed in the Sports Medicine Research Laboratory the order of testing will always occur with Consent and Demographics, Self-reported outcomes, strength, and function & gait.

**Collecting of Recruitment, Inclusion and Retention Rates:** We will determine: 1) the number of patients recruited from various clinics and the frequency of recruitment using different recruitment modes (physician recommendation, mailings or other), 2) the percentage of patients that screen into the study compared to the number recruited, and 3) the percentage of patients retained at the 4- and 8-week post-tests (frequency of reasons for drop-out will be collected).

**Collecting Compliance, Adherence, and Tolerability of the Interventions Data:** We will determine the frequency and percentage of TE sessions that patients complete and record the usage of the TENS and sham TENS units. We will report adherence of all patients to the completion of 12 TE sessions over a 4-week period. A 10cm visual analog scale (VAS) will be used to quantify tolerability.

#### ***Informed Consent***

The informed consenting process will be conducted as outlined in Appendix B, and we will not continue study procedures until written informed consent from the participant is collected.

#### ***Inclusion and Exclusion Criteria & Knee Injury Questionnaire***

Study Inclusion and Exclusion Criteria will have previously been checked as part of a pre-screening measure prior to scheduling the participant. The study participant will physically read and check "yes or no" for each of the exclusion criteria on the first page of the Knee Injury Questionnaire during the screening session. If the

participant has a question he/she can ask study personnel, who will answer the question in a polite and understanding manner. If an exclusion criteria is checked yes the study personnel will talk with the participant and ensure that the answer was not a mistake after asking for an elaboration on the answer. If the exclusion criteria is indeed present the study personnel will explain why the participant can not be enrolled in the study and he/ she will be excluded. If no exclusionary criteria are present the participant will complete the knee Injury Questionnaire and then be provided a Western Ontario and McMaster University Osteoarthritis (WOMAC) Index.

### **Western Ontario and McMaster University Osteoarthritis (WOMAC) Index**

The Participant will be provided a quiet room with a desk and access to an investigator. The participant will fill out all subsections of the WOMAC (Pain, Stiffness and Function). The investigator will score the function section by adding the numbers associated with the various answers. A WOMAC Function score of 23 or higher indicates that the participant is experiencing enough dysfunction to be included in the study. The participant will then undergo quadriceps central activation ratio testing.

**Neuromuscular Activation:** We will assess quadriceps central activation ratio as a representative variable of lower extremity neuromuscular activation. Quadriceps central activation ratio has been demonstrated to be significantly decreased in knee OA compared to healthy, matched controls, and we have reported acceptable measurement reliability ( $ICC_{2,k} = 0.85$ ) over 4 weeks. Quadriceps central activation ratios will be collected as previously reported by the PI using an automated triggered method to improve reliability of this technique.

**Gait Biomechanics:** Peak sagittal plane knee kinematics and kinetics will be collected during the first 50% of stance phase and processed in our 3-dimensional, 10-Camera (Vicon) motion capture laboratory. Gait will be collected at a self-selected speed; speed at pre- and post-tests will be used as a time-dependent covariate

**Physical Function:** Physical function will be measured with the three core performance-based tests (30-s chair-stand test, 40 m fast-paced walk test, a stair-climb tests) endorsed by the Osteoarthritis Research Society International guidelines.

**Physical Activity:** Self-reported physical activity will be quantified using the Physical Activity Scale for the Elderly (PASE), which is a valid tool to assess self-reported participation in physical activities of varying intensities.

**The Self-Efficacy for Physical Activity (SEPA):** The SEPA scale will be used to assess the respondents' confidence in their ability to be physically active despite common barriers (adverse weather, lack of time, when tired, in a bad mood, or on vacation). The SEPA has demonstrated good internal consistency and construct validity as well as acceptable retest reliability (0.9) over 2 weeks.

**Quality of Life, Disease Related Self-Reported Disability, and Visual Analog Scales (VAS):** A paper version of the Short-Form (SF) 12 will be used to quantify the patients' quality of life. A paper version of the WOMAC score will be administered to each patient in a quiet room as previously performed by the PI. The total WOMAC score is useful as a measure of disability, yet important WOMAC subscale information regarding pain, stiffness and disability will also be analyzed separately. Although the focus of this study is TENS use to treat neuromuscular activation, we recognize that it may affect pain and will use the WOMAC pain subscale as a secondary outcome to assess pain. Three separate 10 cm VAS questionnaire will be used to assess the 1) current tolerability of walking, 2) the likelihood to continue the same level of physical activity, and 3) current pain level.

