## **3.e Participant Screening and Eligibility Criteria**

### **3.e.1 Participant Screening**

A study team member will then administer a screening questionnaire via telephone to further assess eligibility. We will obtain participants' verbal consent to ask this limited number of questions. If patients meet telephone screening criteria and are interested in participating, they will be asked to meet a study team member at the Sports Medicine Research Laboratory to complete the consent process.

Following administration of the consent and HIPAA authorization, we will first assess Function with the WOMAC Score and measure height and weight to determine BMI. Next we will complete a burst superimposition test in the involved limb to determine the level of voluntary activation or Central Activation Ratio (CAR). If they do not meet the criteria for WOMAC, BMI or CAR.

If patients are not overweight according to BMI criteria, or if they do not meet clinical criteria for knee OA (and also do not have radiographic evidence of hip or knee OA in at least one joint), they will be excluded from the study.

If participants have knee or hip replacement surgery, their active involvement in the study will end, as these surgeries would likely confound study outcomes including pain and physical function. Also, if female participants become pregnant, their active involvement in the study will end because weight gain would also

likely confound study results. As part of the telephone screening process, women will be excluded if they self-report being pregnant or planning to become pregnant. Women of child-bearing potential will be further tested for pregnancy via urine test at the time of enrollment. This will occur following informed consent. Participants will only be allowed to continue with other study activities once a negative pregnancy test is confirmed. We will consider women to be of child-bearing potential unless they report EITHER having a hysterectomy or ceasing menstruation for at least 2 years. Given the average age of patients with hip and knee OA, we anticipate there will be few instances requiring pregnancy testing. Enrolled women who have had a negative pregnancy test will be informed that they must notify the study team immediately if they become pregnant during their active involvement in the study.

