### **3.e.2 Eligibility Criteria**

All participants must meet the following criteria:

- between the ages of 40 and 75 years old
- All knee OA participants must exhibit symptomatic knee OA, which we will define as a normalized, person based, Western Ontario and McMaster Universities Arthritis Index (WOMAC) function subscale score > 31(out of 100 points, indicating most dysfunction)
- radiographic evidence of tibiofemoral OA (2-4 on the Kellgren – Lawrence scale) 39
- neuromuscular activation deficits, defined as quadriceps neuromuscular activation of less than 90% in the involved leg.

Potential participants meeting any of the following criteria (based on the electronic medical record or in laboratory screening) will be excluded if:

- Diagnosed with a cardiovascular condition restricting exercise
- Have had a corticosteroid or hyaluronic acid injection in the involved knee in the previous 6-months
- Have pacemaker
- Have a neurodegenerative condition
- Have rheumatoid arthritis

- Have cancer
- Have a neural sensory
- Have dysfunction over the knee
- Have a Body Mass Index (BMI) over 35
- Have a history of lower extremity orthopaedic surgery in the past year
- Have a history of a traumatic knee injury in the past 6 months
- Have any history of a total knee arthroplasty in either extremity
- Have a diagnosed, non-reconstructed knee ligament tear.
- Need an assistive device to walk
- Currently pregnant

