## **WOMAC**

The WOMAC will be used to assess self-reported disability. The WOMAC consists of 24 items divided into three subscales which individually assess pain, stiffness and physical function in individuals with knee osteoarthritis. The pain subscale consists of 5 items and assesses the magnitude of knee pain during walking, using stairs, in bed, sitting or lying, and standing. The stiffness subscale consists of 2 items and assesses the magnitude of stiffness after first waking in the morning and later in the day. The physical function consists of 17 items and asks about the magnitude of difficulty when ascending and descending stairs, rising from sitting, standing, bending, walking, getting in / out of a car, shopping, putting on and taking off socks, rising from bed, lying in bed, getting in and out of the bath, sitting, getting on and off the toilet, completing heavy household duties, and completing light household duties. Each item is presented in a 5 point Likert-type format and uses the following descriptors for possible answer choices none, mild moderate, severe, and extreme. Each descriptor corresponds to an ordinal scale of 0-4. The scores are summed for the items in each subscale, with possible ranges as follows: pain=0-20, stiffness=0-8, physical function=0-68. Higher scores on the WOMAC indicate greater amounts of pain, stiffness, and functional limitations.

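### Two screening instructions conflict with the mandatory eligibility list: a raw WOMAC function cut-off of 23 where the list implies 22, and an exclusion of patients who are not overweight that the list does not contain (minor)

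*Combined protocol and SAP*

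**What the plan says.** Section 3.e.2 (Eligibility Criteria) is binding: "All participants must meet the following criteria". On function it asks for a normalised WOMAC "function subscale score > 31(out of 100 points, indicating most dysfunction". It also requires radiographic tibiofemoral OA of Kellgren-Lawrence grade 2-4 and quadriceps activation below 90% in the involved leg. Its only BMI rule excludes values over 35.

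Two other places tell staff how to apply entry rules.

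- **Section 3.i.2, WOMAC Index paragraph.** The investigator adds up the function item scores and applies a raw threshold: "A WOMAC Function score of 23 or higher indicates that the participant is experiencing enough dysfunction to be included in the study". There is no normalising step. Section 3.n.1 (WOMAC) fixes the scale: "The physical function consists of 17 items", "Each descriptor corresponds to an ordinal scale of 0-4", and the range is given as "physical function=0-68".
- **Section 3.e.1 (Participant Screening).** After the WOMAC, BMI and CAR measurements are described, one sentence reads in full "If they do not meet the criteria for WOMAC, BMI or CAR" and stops without a consequence. The next paragraph begins "If patients are not overweight according to BMI criteria, or if they do not meet clinical criteria for knee OA", adds a parenthesis about radiographic hip or knee OA in at least one joint, and says such patients are excluded.

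**The concern.** The manual exists so that every patient is handled by the same rules. Here the list and the working instructions give different answers for the same patient. A raw function score of 22 qualifies under section 3.e.2 and fails under section 3.i.2. A patient of normal weight is acceptable under section 3.e.2 and excluded under section 3.e.1, which gives no BMI value at which a patient counts as overweight.

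What is at stake is who enters the trial and how screening is reported. Section 3.i.2 (Scope) lists the percentage of patients who screen in among those recruited, and section 3.m.1 (Biannual Reporting) includes screening rates and failures. Refusals made on rules that are not in the eligibility list would be counted in those figures. The checks in section 3.m (Study Compliance) would not reveal them, because they cover the first 10 patients found eligible and then the files of randomised patients. Someone wrongly refused is in neither group.

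**Working it through.** **WOMAC function**

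Inputs: 17 items, each scored 0-4 (section 3.n.1, WOMAC); threshold above 31/100 (section 3.e.2); operating cut-off raw 23 (section 3.i.2).

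1. Raw maximum: 17 × 4 = 68, which reproduces the range stated in section 3.n.1.
2. Normalised score = 100 × raw / 68. The threshold in raw points is 0.31 × 68 = 21.08.
3. Scores around the threshold:

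| Raw score | Normalised | Meets list (above 31) | Meets raw 23 or higher |
|---|---|---|---|
| 21 | 30.88 | no | no |
| 22 | 32.35 | yes | no |
| 23 | 33.82 | yes | yes |

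4. The lowest qualifying raw score is therefore 22, not 23. Reading the threshold as at least 31, or rounding the normalised score to an integer and then asking for more than 31, also gives 22.
5. Could 23 be right on some other scale? It is the lowest qualifying score only if 22/M ≤ 0.31 and 23/M > 0.31, that is 70.97 ≤ M < 74.19, so a maximum M of 71 to 74. The stated maximum of 68 lies outside that range.
6. Which normalised threshold X does match raw 23? One with 32.35 ≤ X < 33.82. A threshold of above 33 works, since 0.33 × 68 = 22.44 and the next whole score is 23.

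The two rules differ on exactly one score value, 22, and the operating rule is the stricter one.

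**BMI and OA definition (no arithmetic)**

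| Item | Eligibility list (3.e.2) | Screening text (3.e.1) |
|---|---|---|
| BMI | exclude over 35; no lower limit | exclude if not overweight; no value given |
| OA | radiographic tibiofemoral, grade 2-4 | clinical criteria for knee OA, or radiographic hip or knee OA in at least one joint |
| Failing WOMAC, BMI or CAR | criteria are mandatory | sentence has no consequence |

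On BMI the screening text adds a lower limit that the list does not have, so a patient below that limit gets opposite answers. On OA the screening text is looser: as worded, a patient with radiographic hip OA alone would not be caught by that sentence, although the list would still exclude the patient.

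**The case against.** The strongest reply is that little follows from this. The WOMAC error touches one raw score and errs on the strict side. The overweight rule has no number, and the only BMI value in the supplied text is 35, so staff could not apply a lower limit consistently; the hip-OA wording may be leftover text, though the documents do not say so. The unfinished sentence does little harm, because section 3.e.2 is mandatory and section 3.i.2 says patients with an exclusion criterion are excluded. The study protocol is Appendix A, which is not supplied, so the intended cut-off cannot be known. All of this stands as to weight. It does not reconcile the passages: 22 and 23 cannot both be right, and an exclusion for not being overweight cannot be squared with a list that has no lower BMI limit.

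Some stronger readings are tempting and are not supported.

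- **A third contradiction on injections.** Section 3.j (Medication Restrictions) sets 14 days before screening for injections into the knee or any lower extremity joint; section 3.e.2 excludes an injection in the involved knee within 6 months. A reader might infer a conflict. Section 3.j is a wider concomitant-medication restriction that also runs through the 8-week test. Both rules can be obeyed together, and section 3.i.2 has the criteria checked before the visit is scheduled. At most a cross-reference is warranted.
- **Ineligible patients enrolled.** The WOMAC error cannot do this. The loose OA wording names reasons for exclusion and declares nobody eligible, and the mandatory list still applies.
- **A breach of the equitable-access aim in section 3.e.1.** That aim concerns initial contact by letter and telephone. WOMAC and BMI are assessed later, after consent, so a patient refused on them has already been contacted.

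**Conclusion.** The concern holds for two items, at minor severity. The raw WOMAC cut-off is one point too high for the stated criterion and scale, and patients scoring exactly 22 (32.4/100) are refused although they meet the list. Section 3.e.1 states a BMI exclusion and an OA definition that do not match the list, next to a sentence that does not say what happens on failure.

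The number of patients affected cannot be computed, because the documents give no distribution of WOMAC scores or BMI and no overweight cut-off. The effect on the reported screening percentages is therefore unquantified, and a reader should not infer that it is material. The comparison between arms is not affected: entry is decided before randomisation and the same rules apply to all three groups. No sample-size, power or alpha figure is involved.

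The conclusion assumes that section 3.e.2 is the governing list and that the 0-68 scoring in section 3.n.1 is the one used at screening. It is shown only for the supplied text.

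**What to change.** 1. **Section 3.i.2, WOMAC Index paragraph:** change the raw cut-off from 23 to 22. If 23 is what the investigators intend, leave it, change the criterion in section 3.e.2 to above 33/100, and use 23 in item 2 as well.
2. **Section 3.e.1:** replace the unfinished sentence and the sentence on overweight, clinical criteria and hip OA with the list's rules. Suggested text: Patients will be excluded if raw WOMAC function is below 22 (31/100 or less), BMI is over 35, quadriceps CAR in the involved leg is 90% or higher, or there is no radiographic tibiofemoral OA of Kellgren-Lawrence grade 2-4.
3. **Section 3.j (optional):** add a cross-reference stating that the 6-month exclusion in section 3.e.2 still applies to the involved knee.
4. Check the same rules in the IRB protocol (Appendix A) and on the screening form.

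The cost is a few lines of text and a form check, submitted as a tracked revision as section 2.0 asks. If recruitment has begun, add a review of screen failures with raw WOMAC function of 22 or with not being overweight as the reason.

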### **3.j Concomitant Medications**

All medications that the each patient is currently prescribed or using as well as been prescribed and has taken in during the previous 4 weeks will be collected at the baseline visit. We will also collect data about the medications on a daily basis using a medication log. We will restrict certain medications for the entirety of the study, at certain time points during the study and for a period of time before the screening visit.

### Medication Restrictions

*Corticosteroid injections* into the knee or any lower extremity joint will be restricted for 14 days prior to the screening visit (based on the drug half-life) and throughout the entirety of the study period including the 8-week follow-up test. We will collect information about when the latest corticosteroid injection occurred for each participant at the prior to screening in order to determine when each participant can attend the screening visit.

*Hyaluronic acid injections* into the knee or any lower extremity joint will be restricted for 14 days prior to the screening visit (based on the drug half-life) and throughout the entirety of the study period including the 8-week follow-up test. We will collect information about when the latest hyaluronic acid injection occurred for each participant at the prior to screening in order to determine when each participant can attend the screening visit.

*Prescription Depressants* (Examples: opiates and opioids, barbiturates, tranquilizers and benzodiazepines) will be restricted 4-weeks prior to screening and throughout the study period as these medications may affect the neuromuscular function.

*Prescription Stimulants* (Example: amphetamines) will be restricted 4-weeks prior to screening and throughout the study period as these medications may affect the neuromuscular function.

*Non-steroidal anti-inflammatory drugs (NSAIDs)* will be restricted 24 hours prior to screening or follow-up testing sessions. We will track NSAIDs and instruct patients not to change their NSAIDs usage during the 8-weeks of the study.

*Acetaminophen* will be restricted 24 hours prior to screening or follow-up testing sessions. We will track Acetaminophen and instruct patients not to change their Acetaminophen usage during the 8-weeks of the study.

